## **5.5 Justification for the Design**

Conventional-ultrasound guided prostate biopsies are the most common clinical procedure used for detection of prostate cancer. This technique involves sampling each sextant area of the prostate with one or more needles, with attention to sampling any suspicious hypoechoic lesions in these or other areas of the prostate.

However, conventional-ultrasound does not reliably image cancerous lesions within the prostate, and at least 75% of the time identifies no abnormalities consistent with cancer even in men known to have prostate cancer. Instead, conventional-ultrasound is generally simply used to identify the prostate and help guide systematic 12-core biopsies for the detection of prostate cancer and for the monitoring of prostate cancer in men on active surveillance. The inability to accurately image prostate cancer results in numerous unnecessary biopsies which have associated patient morbidity and increased health care costs.

Improvements in prostate cancer imaging are clearly needed.

mpMRI has been suggested as a means to improve prostate cancer imaging, however this modality may not provide adequate visualization of small lesions due to the poor resolution of mpMRI. Further, a specialized radiologist is required to interpret the imaging and real-time image-guidance is not possible. For these reasons, an office-based real-time imaging solution would be preferred.

micro-US uses high frequencies (29 MHz) to improve resolution of prostate ultrasound images, and provides a protocol for assessing risk in these images known as **PRI-MUS™ (Prostate Risk Identification using Micro-Ultrasound)**. Using this technology, the predecessor of ExactVu was recently demonstrated by a team at Johns Hopkins Medical to have improved ability to image cancerous foci over conventional-ultrasound, and to have potential improved efficacy in identifying higher grade tumors. More recent studies have extended these findings, by providing further evidence of the superiority of micro-US to conventional-ultrasound and preliminary evidence that micro-US may provide similar improvements to mpMRI.

The proposed study will allow direct imaging comparison within the same patient between mpMRI and micro-US to directly compare the sensitivities of these two modalities to prostate cancer.

### **5.5.1 Evaluation of pre-clinical data**

Exact Imaging has not performed pre-clinical testing using animals using the current version of ExactVu. Tests using animals were performed prior to the pilot study described in section 5.5.2.1, using previous generations of the technology used in ExactVu, however these studies were not conducted by Exact Imaging.

## **5.5.2 Clinical evaluation**

### **5.5.2.1 Previous clinical experience: Johns Hopkins Pilot Study**

Johns Hopkins Urology conducted a small scale clinical trial in 2011/2012 using the *previous generation* of the technology used to design and manufacture ExactVu. This trial was conducted to compare the differences between Ultra High Resolution (UHR) and Low Resolution (LR) transrectal ultrasound in their ability to detect cancerous foci in 20 patients.

Patients were imaged pre-operatively with both micro-US and LR-TRUS. Areas of altered echogenicity  $\geq$  5mm on sagittal views were identified by a radiologist with an expertise in ultrasound blinded to pathology results. Actual areas of prostate cancer  $\geq$  5mm identified at sagittally-sectioned RP specimen were correlated to abnormal foci on both imaging modalities. Sensitivity and specificity analysis were performed for each imaging modality. A total of 56 cancerous foci were pathologically identified. micro-US was superior to LR-TRUS in the identification of these foci ( $p = 0.01$ ).

The results of this pilot trial showed significant increases in Sensitivity (56.5%), Specificity (21.1%) and PPV (predictive positive value) (42.0%) with ExactVu versus conventional low resolution ultrasound.

Results of the study were published in *Urologic Oncology*.

### **5.5.2.3 Previous clinical experience: Urology of Virginia Case Series (UHR-2016-001)**

A small 9-subject case series was performed under WIRB protocol 20162036 to provide guidance to clinical users on the appearance of mpMRI lesions visualized with micro-ultrasound. Results from this study were first presented at the EAU 2018 meeting and have recently been accepted for publication in the Canadian Urological Association Journal.

This small series demonstrated superior sensitivity by micro-US (89% vs 56% for mpMRI), particularly against relatively inexperienced mpMRI reviewers and for small Gleason Sum 7 lesions. Both micro-US and mpMRI provided superior targeting sensitivity compared to conventional ultrasound ( $p=0.02$ ). mpMRI lesions were retrospectively visible under micro-US, making it easier to perform accurate targeted biopsy.

#### **5.5.2.4 Previous clinical experience: Reports in the literature from cohort studies**

Cohort studies are available from two European centers demonstrating promising detection rates and sensitivity relative to mpMRI. Astobidea et al. reported on 41 consecutive subjects biopsied using the ExactVu micro-ultrasound system with available mpMRI studies for comparison and targeted biopsy. mpMRI correctly predicted 28/41 subjects with clinically significant prostate cancer (68% sensitivity) while micro-ultrasound predicted 40/41 (98% sensitivity). This improvement in sensitivity was significant with  $p<0.001$ .

Similarly, Lughezzani et al reported on their first 60 subjects with both mpMRI targets and micro-ultrasound guided biopsy as part of their prospectively maintained prostate biopsy database. In this dataset, in which all subjects had positive mpMRI, sensitivity and negative predictive value of micro-ultrasound were 83% and 80% respectively, while the sensitivity of mpMRI was similar at 85%.

#### **5.5.2.5 Literature review**

A critical literature review was performed to establishing incidence, prevalence and cancer detection rates, as further justification for the design of the proposed investigation. The conclusions for the evaluation are presented in section 5.20. (Note that bibliographic references specific to the literature review are also presented in section 5.20.)

### **5.6 Risks and Benefits**

#### **5.6.1 Device risk analysis and management**

The Risk Management Plan for ExactVu and the related hazard analysis was conducted in accordance with ISO 14971 and with reference to Exact Imaging's quality system procedures.

#### **5.6.2 Risks associated with participation in the clinical investigation**

There are no known risks in the use of ultrasound as it will be used in this investigation. There may be slight discomfort caused by the ultrasound probe inserted in a subject's rectum, as in a standard biopsy procedure.

There are some known risks and discomforts associated with a biopsy procedure, however no new risks are introduced by participating in this trial, nor by the use of ExactVu, and known risks are not increased.

Known risks and discomforts associated with biopsy of the prostate include:

- Pain in the biopsy area (rectum area)
- Sudden, complete inability to urinate
- Dysuria (difficulty with urination)
- Urinary tract infection (UTI)
- Prostatitis (infection of the prostate)
- Sepsis (severe whole body infection)

- Hematospermia (blood in the semen or ejaculation fluid)
- Hematuria (blood in the urine)
- Hematochezia (blood in the stool)
- Allergic reaction to lidocaine

There are also known risks and discomforts associated with the MRI procedure, however no new risks are introduced by participating in this trial, and these known risks are not increased. The subjects included in the research will have already received mpMRI as standard of care before enrollment. Known risks and discomforts associated with mpMRI include:

- Allergic reaction to contrast agent (gadolinium chelate)
- Nephrogenic systemic fibrosis due to contrast agent (gadolinium chelate)
- Anxiety due to the confined space
- Tissue burns or damage due to undisclosed presence of metallic implant

### ***5.6.3 Possible interactions with concomitant medical treatments***

No new interactions with concomitant medical treatments are anticipated related to the use of ExactVu. ExactVu is already intended and cleared by FDA to perform the prostate biopsy procedure clinically. ExactVu is designed to introduce no increased risk when compared to conventional ultrasound. An enrolled study subject has already been scheduled for prostate biopsy by his physician.

## **5.7 Objectives and Hypothesis**

### ***5.7.1 Objectives***

**Primary Outcome:** Comparison of subject-level detection rate of clinically significant cancer (csPCa, defined as ISUP 2 or higher) between micro-ultrasound targeted biopsy and mpMRI targeted biopsy.

#### **Secondary (unpowered) Outcomes:**

- Compare lesion size and shape between mpMRI and micro-ultrasound (follow-up with detailed whole-mount pathology when available)
- Compare detailed pathological findings (cribriform structure, density of cancer, subtype of cancer) with imaging findings in both modalities
- Identify percentage of micro-ultrasound lesions (with positive biopsy result) that can be identified retrospectively using mpMRI (requires retrospective re-reading of mpMRI sequences given list of micro-ultrasound targets)
- Identify percentage of mpMRI lesions (with positive biopsy result) that can be identified retrospectively using micro-ultrasound (requires retrospective re-reading of micro-ultrasound sweeps given list of mpMRI targets)

### ***5.7.2 Hypothesis***

**Primary Hypothesis:** Micro-ultrasound provides non-inferior (10% margin) sensitivity to detect csPCa using targeted samples compared to mpMRI.

### **5.7.3 Claims**

There are no claims related to the intended performance of the system that are to be verified in the analysis related to this investigation, aside from those related to the objectives.

### **5.7.4 Risks**

There are no risks or foreseeable adverse device effects that are to be assessed in the investigation.

## **5.8 Design of the Clinical Investigation**

All subjects will receive standard routine care (i.e., prostate biopsy) per standard indications, using transrectal ultrasound guidance. Micro-US can reliably image the peripheral zone of the prostate. This is done in a transrectal approach, as is conventional ultrasound.

### **5.8.1 General**

#### **5.8.1.1 Type of clinical investigation**

The investigation is a study where all subjects have an indication for prostate biopsy. This will allow the most general assessment of the study's main objective which is comparing the imaging quality of micro-US with mpMRI. Each subject will act as their own control in order to make the resulting images as comparable as possible. This multiple-imaging design also reduces the number of subjects needed without substantially increasing risk, subject discomfort, or procedure time.

#### **5.8.1.2 Avoiding bias**

The mpMRI report will be blinded from Operator 1 performing the micro-ultrasound targeted and systematic biopsies, to avoid biasing identification of suspicious regions on micro-US. Operator 2 will have full knowledge of the mpMRI report and images, but will not observe the micro-ultrasound targeting portion of the procedure or see the resulting target locations. Separate operators will complete the two phases of the procedure to avoid bias from the micro-ultrasound targets interfering with biopsy site selection for mpMRI targets.

#### **5.8.1.3 Endpoints**

##### **Primary endpoint**

The primary endpoint is the presence of clinically significant prostate cancer (csPCa) in each subject. The per-subject presence of cancer will be determined based on a positive biopsy from any sample, targeted or systematic. Patient-level sensitivity for a given imaging modality will be determined through systematic biopsy results plus targeted samples taken using only that modality. In this way we approximate clinical reality of using a given modality for systematic plus targeted biopsy.

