##### **Secondary endpoints**

Sensitivity of targeted-only samples for each modality will also be calculated in order to determine the effectiveness of a targeted only biopsy technique in each case. Presence of cancer per-target will also be assessed, along with detailed pathological findings, and targeting modality identifying the lesion. Size and shape of lesions will also be recorded from recorded images.

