#### Non-inferiority Margin, $\delta$

In the PROMIS study, the most recent confirmatory study of mpMRI to TRUS, mpMRI showed improvement in sensitivity of MP-MRI to TRUS from 0.93 to 0.48, respectively, with a test ratio of 0.52 (95% CI: 0.45-0.60) using McNemar's test. In order to preserve the effect of mpMRI versus TRUS as seen in this study, the non-inferiority margin for the test ratio of 0.76 (24%) was chosen as being equal to 50% of the effect from the point estimate of 0.52 to a ratio of unity (equal sensitivity). Then, the lower bound of the test ratio must not exceed 0.76 in order for non-inferiority to be declared in the current trial, thus preserving at least 50% of the effect of mpMRI versus TRUS. McNemar's test will be used to establish the (1- $\alpha$ ) confidence interval for the test ratio.

Specificity from the same study was lower on mpMRI than TRUS with a test ratio of 2.34 (2.08–2.68). In the prostate biopsy procedure, since sampling is required regardless of imaging outcome (systematic sampling), specificity is less important. Still, we would like to preserve a reasonable specificity similar to mpMRI, therefore we select a non-inferiority margin of 0.67, or not more than 50% worse than the existing difference between mpMRI and TRUS (2.34\*1.5 ratio to TRUS, 1/1.5=0.67 ratio to mpMRI).

Details of the design are presented in section 5.8.1.

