### **5.9.5 Pass/fail criteria**

The primary outcome of the study will fail if micro-ultrasound targeted biopsy fails to identify cancer in significantly more subjects than mpMRI targeted biopsy. This will be quantified by testing against the lower one-sided 95% confidence interval bound of the ratio of the two sensitivities, which must not be less than 76%.

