Two recent studies were found that investigated rates of successfully targeting prostate cancer with greyscale LR-TRUS using biopsy as the reference standard, all other studies were pre-1990 and are considered less relevant due to substantial improvements in imaging technology. These studies vary considerably in the aggressiveness of their targeting, with Barish et al. demonstrating a sensitivity of 40% (specificity 80%, N=544) and Nelson et al. a sensitivity of only 26% (specificity 89%, N=137). Weighted average sensitivity and specificity are 37.2% and 81.8% respectively. This sensitivity value is very close to that found during our pilot study against the more accurate radical prostatectomy (RP) reference (37.7%), however the specificity value in that study was much lower (65.4%). This may be due to the low N=25 of that study, or the greater accuracy of the RP reference. If micro-US provides a more accurate biopsy reference (closer to RP), we may expect a specificity between 81.8% and 65.4%. The PROMIS trial did not test targeted biopsy on LR-TRUS, but did report the sensitivity of systematic biopsy using LR-

TRUS to detect prostate cancer. This value is reported as 48%, which demonstrates the value of the additional systematic biopsy cores due to the poor sensitivity of targeted only sampling using this modality. This higher value will be used to define the non-inferiority threshold, in order to be as rigorous as possible.

The PROMIS trial provides the highest quality evidence of prevalence in this population, using template mapping biopsy to demonstrate clinically significant cancer in 308/572 subjects (54%). This is a reasonable value given other meta-analyses demonstrating detection rates from 24%-87% in the literature.

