Sensitivity of mpMRI has varied widely in the literature as demonstrated by numerous meta-analyses, showing detection rates ranging from 24%-87%. The PROMIS trial found a sensitivity of 88% for predicting clinically significant prostate cancer, but did not perform targeted biopsy. Therefore, this value could be seen as a maximum possible when perfect targeting and histopathology is assumed. In cases with targeted biopsy, such as the PRECISION trial, mpMRI detected significant cancer in 38% of the arm vs. 26% in the systematic biopsy arm. Assuming a similar 54% incidence this amounts to sensitivities of 70% and 48% respectively which compare well with our own feasibility cohorts demonstrating sensitivities of 56-85% for mpMRI and previously discussed sensitivity data for systematic biopsy.

Sensitivity data on micro-US is available from 2 cohort studies and 1 randomized trial. These three datasets suggest sensitivities of 83% (N=60), 98% (N=79), and 61% (N=286) for a weighted average of 71%. While this average is biased towards the earlier data from the randomized trial, this study was conducted on an early version of the device with little training on the PRI-MUS risk identification protocol, therefore we expect this to underestimate the true sensitivity of the micro-US modality.

Given an incidence of approximately 50% with sensitivities of mpMRI and Micro-US of approximately 66% and 75% respectively, 108 subjects are required to provide 80% confidence of achieving non-inferiority within 20%. This non-inferiority bound was chosen to maintain at least 50% of the benefit of mpMRI over conventional systematic biopsy providing a sensitivity of approximately 48%.

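### The primary endpoint is defined on two different core sets, and sharing systematic cores between the modalities weakens the test of the stated targeting hypothesis

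*Combined protocol and SAP*

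**What the plan says.** The sections that state the question use targeted cores:

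- 5.7.1, primary outcome: detection of clinically significant cancer is compared "between micro-ultrasound targeted biopsy and mpMRI targeted biopsy".
- 5.7.2, primary hypothesis: "Micro-ultrasound provides non-inferior (10% margin) sensitivity to detect csPCa using targeted samples compared to mpMRI".
- 5.9.5, pass/fail: the trial fails if "micro-ultrasound targeted biopsy fails to identify cancer in significantly more subjects than mpMRI targeted biopsy". This is then quantified as a one-sided 95% lower bound on the sensitivity ratio that may not fall below 76%.

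The section that defines the endpoint does not. Under 5.8.1.3, "Patient-level sensitivity for a given imaging modality will be determined through systematic biopsy results plus targeted samples taken using only that modality". The reason given is that this approximates clinical use. The secondary endpoints then add: "Sensitivity of targeted-only samples for each modality will also be calculated". The two definitions stand next to each other, so the combined one is deliberate.

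Neither 5.9.1 (hypotheses) nor 5.9.3 (power at 0.85 against 0.90) names a core set. Section 5.4.6 describes one systematic set, taken by Operator 1 after the micro-ultrasound targets.

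On the margin, 5.9.1 says "the non-inferiority margin for the test ratio of 0.76 (24%) was chosen" as half the distance from 0.52 to 1. The 0.52 compares systematic TRUS biopsy (0.48) with mpMRI (0.93). Section 5.20 says of the 48% systematic figure: "This higher value will be used to define the non-inferiority threshold". It also notes that the source trial found a high mpMRI sensitivity "but did not perform targeted biopsy".

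**The concern.** An analyst following the objective, hypothesis and pass rule would analyse targeted cores. An analyst following the endpoint definition would analyse systematic plus targeted cores. Nothing in 5.9 says which governs, and the two can give opposite verdicts on the same data.

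The combined version is the easier one to pass when micro-ultrasound targeting is worse. A positive systematic core turns a man found only by mpMRI targeting, or missed by both, into a man detected by both. The ratio moves toward 1 and the discordant count that drives its standard error shrinks. A result described as confirming 5.7.2 could then rest largely on cores that neither modality targeted.

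The margin does not settle the matter. It compares mpMRI alone with systematic biopsy alone, not two strategies that share systematic cores. Its source trial took no targeted cores, so it needs a stated rationale for a targeted-only endpoint as well. The targeted-based sections also disagree with each other: a 10% margin in 5.7.2, superiority wording in 5.9.5, and a 0.76 ratio bound.

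**Working it through.** **The plan's own figures.** The margin reproduces: 0.52 + 0.5 × (1 − 0.52) = 0.76. The sample size does not. With a paired log-ratio formula, one-sided 0.05, 80% power and 20% discordance, cases needed = (1.645 + 0.842)² × [0.20/(0.85 × 0.90)] / [ln(0.85/0.90) − ln 0.76]² ≈ 6.185 × 0.2614 / 0.0472 ≈ 34.2. That is 35 cases, or 35/0.60 ≈ 59 subjects; a score test gives about 77. The 120 is therefore more than the stated inputs need. That is a separate point, and it does not show which core set was meant.

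**Inputs**

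- Cases: 0.60 × 120 = 72 (5.9.1) or 0.54 × 120 ≈ 65 (prevalence in 5.20).
- Systematic sensitivity S = 0.48 (5.20). This is a conventional-ultrasound figure from another trial, so it is an assumption here.
- mpMRI-targeted sensitivity m = 0.70 (5.20), with 0.90 (5.9.3) as an alternative.
- Micro-ultrasound-targeted sensitivity u, varied.

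**Model.** Under independence, with shared systematic cores:

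- detected by both: S + (1 − S)mu
- micro-ultrasound only: (1 − S)u(1 − m)
- mpMRI only: (1 − S)m(1 − u)

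Targeted-only is the same with S = 0. The trial passes if exp[ln R − 1.645 √((b + c)/(xy))] > 0.76, where R is the sensitivity ratio, b and c are the discordant counts, and x and y are the positives per modality. Each case used 400,000 simulated trials.

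**At the margin.** u = 0.76 × 0.70 = 0.532. The combined sensitivities are 0.48 + 0.52 × 0.532 = 0.757 and 0.48 + 0.52 × 0.70 = 0.844, a ratio of 0.896.

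| u | Targeted ratio | Combined ratio | Pass, combined (65/72 cases) | Pass, targeted-only |
|---|---|---|---|---|
| 0.532 | 0.76 | 0.896 | 67/71% | 5.5/5.6% |
| 0.45 | 0.64 | 0.846 | 38/41% | 0.4/0.3% |
| 0.31 | 0.44 | 0.76 | about 7% | about 0% |
| 0.20 | 0.29 | 0.69 | under 1% | about 0% |
| 0 | 0 | 0.57 | 0% | 0% |

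The combined ratio falls to 0.76 only when u = (0.76 × 0.844 − 0.48)/0.52 = 0.31. Restricting cases to men positive on any core, as 5.8.1.3 does, gives 69/73% in the first row.

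**Range at a true targeted ratio of 0.76**

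- S = 0.35: 41-44% (m = 0.70) and 51-54% (m = 0.90). S = 0.80: over 99% for both.
- Positive dependence among the three core sets, S = 0.48, latent correlation 0.3/0.5/0.7: 61-64/56-58/48-51% at m = 0.70, and 57-61/43-45/27-28% at m = 0.90. Targeted-only stays at 6-7%.
- S = 0.35, m = 0.90, correlation 0.7: about 15%, against 7%.

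**The case against.** **The size is not known.** What matters is how often systematic cores are positive in men whom mpMRI targeting finds and micro-ultrasound targeting misses, and the documents do not give this. Independence sets it at 0.48. In the correlated model with m = 0.90 and correlation 0.7 it is about 0.19. With systematic sensitivity 0.26 and the same dependence, the trial passes about 10% of the time against 7%. This stands: 67-71% is illustrative. The direction does not depend on it whenever systematic cores find some of the men that micro-ultrasound targeting misses and micro-ultrasound is the worse modality.

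**It is a different estimand, not an inflated type I error.** A combined ratio of 0.90 really is above 0.76, so passing is correct for the combined question. Section 5.8.1.3 gives a reason for asking that question, and the targeted-only figures will be reported. This also stands, and a consistently stated strategy comparison would be defensible. It is not the hypothesis in 5.7.2, however, and a secondary endpoint does not decide the trial.

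**The margin may suit the combined strategy.** Section 5.20 does give some reasoning, including targeted-biopsy data and the aim of keeping half the benefit over systematic biopsy. The same half-effect recipe applied to systematic-plus-mpMRI against systematic alone, under independence, gives (0.48/0.844 + 1)/2 = 0.78 at m = 0.70 and (0.48/0.948 + 1)/2 = 0.75 at m = 0.90. A number near 0.76 might therefore survive, but the plan has not derived it for that comparison.

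**The systematic set may depend on the targets.** If micro-ultrasound targets use up part of the 12-core count in 5.4.6, the systematic result depends on one modality more than the other, and the model above is too simple. This is a further reason to define the set.

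**Conclusion.** The concern holds. The contradiction is explicit in the text, and 5.9.1 and 5.9.3 do not resolve it. If 5.8.1.3 is followed, a pass does not support the targeting claim in 5.7.2. With micro-ultrasound targeting exactly at the margin, the chance of passing is 67-71% under the central assumptions (systematic 0.48, mpMRI-targeted 0.70, independence), against about 5.5% on targeted cores. Across the main alternatives it runs from about 15% to over 99%, and to about 10% with a systematic yield lower still. It exceeded the targeted-only rate in every case tried. The test can still be lost: micro-ultrasound with 20% targeted sensitivity passes less than 1% of the time. This must be settled before results are seen, because it determines what the only powered test can conclude.

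**What to change.** Name one core set for the primary test, identically in 5.7.1, 5.7.2, 5.8.1.3, 5.9.1, 5.9.3 and 5.9.5.

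- **To answer 5.7.2:** make the primary endpoint clinically significant cancer in that modality's targeted cores only. Count men with no target on a modality as not detected by it. Report systematic plus targeted as secondary, without the 0.76 margin.
- **To keep the combined strategy:** rewrite 5.7.1, 5.7.2 and 5.9.5 to say so, and derive a margin for that comparison.

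In the same amendment:

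1. Reconcile the 10% margin in 5.7.2 and the superiority wording in 5.9.5 with the 0.76 bound, and state why the bound kept suits the chosen core set.
2. Reconcile 5.4.6, where systematic cores are taken up to a count of 12, with 5.8.6, which expects 12 systematic cores, so that the systematic set is defined.
3. State which core set the 0.85 and 0.90 in 5.9.3 describe, and recompute power for the chosen endpoint.

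**Cost.** This is wording plus a swap of primary and secondary. Targeted lesions already go in separate jars, so no extra cores are needed. Power is the real cost. Against 0.76, targeted-only power is:

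- 0.85 vs 0.90, 72 cases, 15/20/25% discordance: about 98/96/92%.
- 0.71 vs 0.70, 65 cases, 20/30/40% discordance: about 97/90/83%.
- 0.66 vs 0.70, 65 cases, 20/30/40% discordance: about 82/69/59%. This keeps the plan's ratio of about 0.94.

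More subjects may therefore be needed. If the 10% margin is the one kept, power at 0.85 vs 0.90 with 72 cases and 10-25% discordance is only 19-36% as a ratio bound of 0.90, or 22-43% as a 10-point difference.
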